**2. EXPEDITED REVIEW CATEGORY**

	SURVEYS, INTERVIEWS, OR PROGRAM EVALUATIONS					
This minimal risk study involves:						
 Research on individual or group characteristics or behavior (including, but not limited to, research on perception, cognition, motivation, identity, language, communication, cultural beliefs or practices, and social behavior).						
 Research employing survey, interview, oral history, focus group, program evaluation, human factors evaluation, or quality assurance methodologies.						
NOTE: Some research in this category may qualify as exempt and some may not be considered human research. See the Exempt Protocol form or the Non-research/Non-human Research form.						

**3. RESEARCH PLAN**

Purpose of Study:						
This research seeks to identify if the practice of the SMART program mindfulness decreases stress and increase resilience in family medicine residents.						

Hypotheses, Research Questions, or Objectives:						
---	--	--	--	--	--	--

- Null Hypothesis 1: There is no significant correlation between SMART program mindfulness training program and increased resilience, decreased stress, and increased overall quality of life for residents.
- Alternative Hypothesis 1: There is significant correlation between SMART program mindfulness training program and increased resilience, decreased stress, and increased overall quality of life for residents.

#### **Significance:**

The hope is that the residents trained will be able to utilize and continue to practice the skills learned throughout their careers as physicians, and thus be able to provide sustained, compassionate care. The research could serve as a pilot project for future studies with larger numbers of residents, and possibly lead to implementation of the program in residencies.

In order to provide optimal patient care, the physician must be healthy and resilient. By practicing mindfulness, the resident should be able not only to successfully handle the everyday stressors of residency, but to enhance his or her ability to learn effectively and improve interpersonal relations.

#### **Military Relevance:**

Resilience is a valued, necessary trait for every military member. The more resilient the airman, the better able to serve the mission.

#### **Background and Review of Literature:**

Historically, mindfulness has its roots in Buddhism. The idea is to reduce stress and increase resilience by daily mindful practice. The SMART program specifically targets busy professionals who could very much use the benefits of mindfulness, but may not have a large amount of time to spend in training. The program uses techniques of joyful and kind attention, as well as a number of methods of interpreting the external world, which when practiced regularly in small increments can add up to increased quality of life.

Residents are pushed to excel in academic and clinical settings, and when combined with their extracurricular responsibilities, this can result in a great deal of stress. Their time is limited, and therefore SMART training may be well suited for their needs. John Kabat-Zinn is generally recognized as one of the foremost authorities on mindfulness, and his article "Mindfulness in Medicine" notes that premedical and medical students benefited from training, showing "reduced psychological distress and increased empathy". He also mentioned a possible link in reduction of medical errors and increased attention.

There is a physiological basis of mindfulness training. Research shows impact in areas of memory, learning, and emotion, as well as visual and auditory sensory regions. The article "Mindfulness Practice Leads to Increases in Regional Brain Gray Matter Density" shows just that, with increased density in areas of the left hippocampus, posterior cingulate cortex, temporo-parietal junction, and cerebellum^2. Another article claims "enhanced attentional regulation of alpha in primary somatosensory cortex", in other words more control over mind wandering.

Used well, the SMART tool would ideally decrease rates of burnout and increase patient safety. Decreased burnout has been linked to mindfulness, and "it has been suggested that increased clinician mindfulness could also reduce medical errors, but there has been no empirical test of this hypothesis". [name] at Mayo Clinic, the creator of the SMART method, notes "in general, peace, joy, and resilience correlate with increased activity in the higher cortical center of your brain, especially the pre-frontal cortex". Mindfulness training can effectively retrain the brain to think differently, to experience life in a more optimistic manner and increase the ability to handle stressors. There are many existing studies evaluating various methods of mindfulness, however the SMART method has not yet been tested on military medical residents.

#### 4. RESEARCH DESIGN AND METHODS

##### **Research Design and Methods:**

The study design will be a one-arm case study, pre and post test design. Active Duty Family Medicine Residents age 18 years or older will be recruited at Eglin AFB. Subjects meeting the inclusion/exclusion criteria will be offered an opportunity to participate.

##### **Screening:**

- Obtain and document signed Informed Consent document and HIPAA Authorization.
- Record: name, age, gender, current email address, phone number, and post graduate year in training.

The Research staff will then contact the subjects to have them complete a follow-up questionnaire. All information collected on the questionnaires will be coded with an identifier and only the research staff will have the Master Key that can be linked back to each individual.

##### **Visit 1-Baseline (can be the same day as Screening Visit):**

- Participants will be handed the following questionnaires in a plain manila envelope to complete prior to the SMART 1 Hour Session and will be asked to return them to the study staff:
  - Stress Scale
  - Mindful Attention Awareness Scale
  - Connor-Davidson Resilience Scale
- Participants will participate in the 1 hour SMART Program training conducted by the PI, who is certified to teach this method.

##### **Visit 2-12 Weeks from Baseline:**

- Participants will be handed the following questionnaires in a plain manila envelope to complete and will be asked to return them to the study staff:
  - Stress Scale
  - Mindful Attention Awareness Scale
  - Connor-Davidson Resilience Scale

##### **Visit 3-12 Months from Baseline:**

- Participants will be handed the following questionnaires in a plain manila envelope to complete and will be asked to return them to the study staff:
  - Stress Scale
  - Mindful Attention Awareness Scale
  - Connor-Davidson Resilience Scale

Subjects' participation ends at 12 months.

##### **a. Interventions and Observations:**

Identify if the practice of the SMART 1 hour training lecture program mindfulness in family medicine residents decreases stress and increases resilience.

##### **b. Setting:**

Eglin Family Medicine Residency Conference Room

c. Date(s):						
September 2018 through September 2020						
d. Subjects:						
Male and Female Active Duty military Family Medicine Residents age 18 years or older at Eglin Air Force Base.						
e. Inclusion/Exclusion Criteria:						
Inclusion Criteria	Male and female active duty military family medicine residents age 18 or older, amenable to participation in training and filling out questionnaires					
Exclusion Criteria	Unwilling to participate					
f. Source of Research Material:						
Will you be using private information in this study?			 Yes name, email address, phone number			
Use of identifiers with private information						
Identifiers to be Used?	Column A Looked at by research team	Column B Recorded on enrollment log, subject list, or key list	Column C Recorded on data collection tool (survey, spreadsheet, etc.)	Column D Recorded on specimen containers	Column E Shared w/ others not on research team	Column F Stored after study ended
Names						
Study codes linked to individuals' identities using a key only accessible by the researcher						
Dates (except year)						
E-mails						
Phone numbers						
Coding Plan?						
Describe the method that will be used to create and assign unique study codes to data.	All information collected on the questionnaires will be coded with an identifier. The code will be placed in a Master Key of identifiable PHI/PII for each subject. The key is linked to a participant's name, email address, and phone number and will be used only to contact subjects to complete their follow-up questionnaires and merge their baseline and post-questionnaire results. Only the research staff will have direct access to the Master Key and be able to link a subject's response to their questionnaire information.					
Describe the method that will be used to create and assign unique study codes to specimens.	 N/A, not collecting specimens					
What is the format of the key?	 Electronic					
Who will have access to the key?	Research Staff listed on this study					
Where will the key be stored and how will it be protected?	
Location(s): We will maintain a Master Key of identifiable PHI/PII that will be kept in an electronic database, which will be encrypted, double password protected and the access will be restricted. The Master Key will be electronically stored separately from the coded de-identified research data. The Master Key will not be stored on any non-government or personal computers or laptops. At the conclusion of the study, the data from Eglin will be de-identified prior to review and analysis.
 
Confidentiality measures: The coded research data will be kept in a locked cabinet in a locked office and only the research department has the key. The coded research data will be retained until the conclusion of the research study. Once a Final Report has been approved by the IRB, all the paper records will be de-identified and any key linking the subject to their records will be destroyed, based on AFI 33-332, "The Air Force Privacy and Civil Liberties Program" and the National Institute of Standards and Technology Special Publication (NIST SP 800-88) for the approved methods to destroy PII. The anonymized
					

	research data will not be utilized for further research activity beyond the protocol stipulations without additional IRB approval and research subject authorization.		
--	---	--	--

**Complete the table.**

Source of Research Material per Participant (Procedures)	# Routine Care	# Research Driven	# Total Procedures
Mindful Attention Awareness Scale	0	3	3
Perceived Stress Scale	0	3	3
Connor-Davidson Resilience Scale	0	3	3

**Instrumentation:**

- Mindful Attention Awareness Scale: Dispositional mindfulness, i.e. open or receptive awareness of and attention to what is taking place in the present
- Perceived Stress Scale: Measures perception of stress as related to life situations.
- Connor-Davidson Resilience Scale: Measure of stress coping ability.

**5. HUMAN SUBJECT PROTECTION**

**Recruitment and Consent Processes:**

Male and Female Active Duty military Family Medicine Residents will be recruited through announcements at morning meetings. All potentially eligible patients, will be offered an opportunity to participate.

**Consent Processes:**

Informed Consent (ICD) and HIPAA Authorization (HIPAA) will be sought in advance from each prospective subject and appropriately documented in accordance with 32 CFR 219.117. The research staff will provide a written copy of the Informed Consent Document and HIPAA Authorization. The subject may decline to consent without prejudice. At the subject's discretion, they may take the ICD and HIPAA home to discuss further prior to making a decision. If the subject consents, a copy of the ICD will be given to the subject. No vulnerable populations are included in this research study. Subjects who cannot provide Informed Consent will not be allowed to participate. No Legally Authorized Representatives (LAR) will be utilized.

Recruiting Service Members	Will you be recruiting service members in a group setting?	 Yes	 No
-----------------------------------	--	---	-----------------------------

**Participation Compensation:**

Subjects will not be paid for participation in this study.

**Assent Process:** N/A

**Benefits:**

The benefits to the participant are increased resilience and decreased stress, and an increased ability to handle issues in both professional and personal life. Long term benefits for research community include data about the effectiveness of the SMART program, and mindfulness training effectiveness among family medicine residents.

**Risks:**

There is a minimal risk of psychological discomfort that may arise during group sharing. Additionally, a slight risk of inadvertent breach of confidentiality is present. The risks of the study are no more than those encountered in daily life.

**Costs:** N/A

**Safeguards for Protecting Information:**

**Data and Specimen Storage Plan**

**How will coded or identifiable data/specimens be stored?**

	Paper data, including completed consent forms	The surveys will only contain the subject number to mask the identity of the individual. The research consents and HIPAA Authorization Documents will be stored in a locked cabinet in a locked room with restricted access.
-------------------------------------	---	--

	Electronic data	All coded, de-identified research data will be electronically stored separately from the Master Key of identifiable patient demographics and PHI/PII.
	Long-term storage (following completion of the study and inactivation of IRB approval)	The research data will be coded and any links to identifiable data will be destroyed (an approved shredding bin) as soon as possible or no later than at the closure of the study. The anonymized research data will not be utilized for further research activity beyond the protocol stipulations without additional IRB approval. All de-identified research data will be maintained for 3 years following study closure.

**Safeguards for Protecting Subjects Relative to Reasonably Expected Risks:**

There is a slight chance of a breach of confidentiality since the designated research coordinator is storing a Master Key of Personally Identifiable Information (name, email address, and phone number).

**Clinical Care:** N/A**Injury Compensation:** N/A**Data Safety Monitoring**  N/A – none of the situations listed above apply**6. DATA ANALYSIS****Data Analysis:**

All questionnaires will be scored according to the mechanism contained within. These scores are considered outcome variables and will be analyzed using paired t-test and repeated measures analysis.

**Outcome Measures:**

Resilience score, stress score, and mindfulness score measured at baseline, 12 weeks, and 12 months will be used as outcome measures.

**Sample Size Estimation/Power Analysis:**

The sample size was estimated based on the medium effect size (0.6, a resilience score mean change = 3, SD = 5) for a 2-sided paired t-test with a significance level  $\alpha$  of 0.05. Taking 20% withdrawal into account, 35 subjects (29 completed) will achieve 80% power.

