**Statistical Analysis:**

Continuous variables will be assessed for normality by the Shapiro-Wilks test. Normally distributed continuous data will be presented as mean and standard deviation. Paired t-tests will be performed to compare the baseline outcome scores with the 12-week outcome scores. The repeated measures analysis with a Bonferroni post hoc test will be performed to determine significant differences over time (i.e., baseline, 12 weeks, and 12 months). Non-normally distributed data will be presented as median and interquartile range (IQR) and will be analyzed using Wilcoxon signed rank test and Friedman's Rank Test (non-parametric methods). A significance level will be set to  $p < 0.05$ . Statistical analyses will be performed by the 59MDW Biostatistician using SAS version 9.4 (Statistical Analysis Software, Cary, NC).

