**Number of Subjects:**

	# Planned to Enroll	# Enrolled	# Planned to Complete Study	TOTAL
Number of Subjects at Eglin AFB	35	0	29	35

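### The sample-size statement does not reproduce: its inputs need 24 completers for 80% power, 29 give about 88%, and 20% withdrawal from 35 leaves 28

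*Combined protocol and SAP*

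**What the plan says.** Under Sample Size Estimation/Power Analysis, the protocol bases its sample size on a "medium effect size (0.6, a resilience score mean change = 3, SD = 5"), "for a 2-sided paired t-test with a significance level" of 0.05. It then concludes: "Taking 20% withdrawal into account, 35 subjects (29 completed) will achieve 80% power". That paragraph names no visit and no adjusted alpha.

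Under Statistical Analysis, the paired t-test is assigned to one comparison: "Paired t-tests will be performed to compare the baseline outcome scores with the 12-week outcome scores". Bonferroni is mentioned there only as a post hoc test following the repeated measures analysis over the three time points.

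The Number of Subjects table, in the row "Number of Subjects at Eglin AFB", repeats 35 planned to enrol and 29 planned to complete the study.

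**The concern.** The paragraph supplies everything needed to check it: test, sidedness, alpha, effect size, withdrawal rate, enrolled number, completers and power. A paired t-test with an effect of 0.6 should reach 80% power with somewhat more than 20 pairs, so 29 looked too many. In addition, 29 of 35 is not 80%.

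This is the only power statement in the plan. If the figures do not follow from the inputs, either an input is misreported or the calculation is wrong, and the reader cannot tell which. That decides whether the planned number carries a margin of several points of power or none at all.

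**Working it through.** **Inputs** (all from Sample Size Estimation/Power Analysis): mean change 3, SD 5, effect size 0.6, two-sided paired t-test, alpha 0.05, 20% withdrawal. Since 3/5 = 0.6, SD 5 is read as the SD of the paired change.

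**Formula.** For n pairs and standardised effect d, the paired t statistic has a noncentral t distribution with n − 1 degrees of freedom and noncentrality d√n. Power is the probability that it falls outside ±t(1 − α/2, n − 1).

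**Attempt to reproduce 29 completers at 80%**, with d = 0.6 and two-sided alpha 0.05:

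| Completers n | Noncentrality 0.6√n | Critical t | Power |
|---|---|---|---|
| 23 | 2.88 | 2.074 | 78.5% |
| 24 | 2.94 | 2.069 | 80.4% |
| 28 | 3.17 | 2.052 | 86.4% |
| 29 | 3.23 | 2.048 | 87.7% |
| 35 | 3.55 | 2.032 | 93.2% |

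The smallest n with at least 80% power is 24. The stated 29 is five more, and the power at 29 is 7.7 points above the stated 80%. Simulation with 200,000 replicates agrees: 80.5% at 24, 86.5% at 28 and 87.7% at 29.

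**Other readings of the same inputs.** None gives 29:

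- Normal approximation: ((1.960 + 0.842)/0.6)² = 21.8, so 22.
- One-sided test: 19.
- Wilcoxon signed rank test: about 25 to 26, and at most 28 at its worst-case efficiency (24/0.864 = 27.8).
- Target of 85% power: 27. Target of 90% power: 32.

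**Withdrawal.**

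- 35 × 0.80 = 28 completers.
- 29/35 = 82.9%, which is a 17.1% loss.
- 29 completers at 20% withdrawal would need 29/0.80 = 36.25, so 37 enrolled.
- 24 completers at 20% withdrawal would need 24/0.80 = 30 enrolled.

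**Routes that do arrive at 29.** At least three fit, and the document supports none of them over the others:

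- Two-sided alpha 0.025: 80.0% power at 29, and 78.4% at 28.
- Inflating by 20% twice: 24 × 1.2 = 28.8, so 29; then 29 × 1.2 = 34.8, so 35.
- Alpha 0.05 with a smaller effect of about 0.54: 29 completers are needed.

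The first contradicts the stated alpha and the third the stated effect size. The second counts the withdrawal allowance twice.

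**Margin at the stated alpha.** With 35 enrolled, 80% power holds while 24 remain, so 11 of 35 (31.4%) can be lost. With 28 completers the detectable effect at 80% power is 0.549. That is a change of 0.549 × 5 = 2.75 points at SD 5, or an SD of change up to 3/0.549 = 5.46 for a change of 3.

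**The case against.** The strongest reply is that nothing is at risk. Read as at least 80%, the sentence is true for both 28 and 29 completers on its own inputs, and a margin above 24 also covers the Wilcoxon fallback. This is right about the consequence, and it is why the point is minor. It does not rescue the statement, which presents 35 and 29 as the numbers derived for 80% power; the plan does not give the fallback as a reason for a margin.

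Second, multiplying 29 by 1.2 gives 34.8, so the 35/29 pair fits a common inflation shortcut. That probably explains the pair, but not the 29, and 29 of 35 is still not 20% withdrawal. Alone, this one-subject gap would be trivial.

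Third, calling the error conservative presumes that 0.05 is the intended alpha. This stands as a condition. If 0.025 was meant, 29 completers give exactly the target and 28 fall just short at 78.4%.

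Fourth, the table counts those who complete the study, which ends at 12 months, whereas the paired t-test is at 12 weeks, when fewer may have been lost. That is also fair. Using 28 for the 12-week test is then a cautious figure.

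**Conclusion.** The concern holds and is minor. On the stated inputs, 80% power needs 24 completers and 30 enrolled, not 29 and 35. The stated 80% is about 6 points too low for 28 completers and about 8 points too low for 29. The completer count is one too high for 20% withdrawal from 35.

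This rests on reading SD 5 as the SD of the change, which the ratio 3/5 = 0.6 supports, and on alpha 0.05 as written. Under those assumptions the 12-week resilience comparison is not underpowered. Where 29 came from cannot be settled from the text. The conclusion does not extend to the Bonferroni post hoc comparisons, for which the plan states no power.

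**What to change.** Keep enrolment at 35 and make three edits:

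1. State the calculation behind 29: the alpha, the effect size and the formula used for the withdrawal allowance.
2. If the stated inputs stand, rewrite the sample-size sentence along these lines: with 35 enrolled and 20% withdrawal, 28 complete; a two-sided paired t-test at alpha 0.05 for a resilience change of 3 (SD of change 5) from baseline to 12 weeks has about 86% power. If a smaller alpha was the basis, give it with its own power instead; at 0.025 that is 80% with 29 completers and 78% with 28.
3. Change planned completers in the Number of Subjects table from 29 to 28. If 29 is kept as the intended count, correct the withdrawal rate to 17.1% so that the two places agree.

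If power is also quoted for the post hoc comparisons, label it conditional. With 28 completers, an effect of 0.6 for each comparison and separate paired error terms, it is about 78% for two comparisons (alpha 0.05/2) and 73% for three (alpha 0.05/3).

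The cost is a sentence or two of protocol wording and one table entry, with no extra subjects and no change to the analysis.

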**Statistical Analysis:**

Continuous variables will be assessed for normality by the Shapiro-Wilks test. Normally distributed continuous data will be presented as mean and standard deviation. Paired t-tests will be performed to compare the baseline outcome scores with the 12-week outcome scores. The repeated measures analysis with a Bonferroni post hoc test will be performed to determine significant differences over time (i.e., baseline, 12 weeks, and 12 months). Non-normally distributed data will be presented as median and interquartile range (IQR) and will be analyzed using Wilcoxon signed rank test and Friedman's Rank Test (non-parametric methods). A significance level will be set to  $p < 0.05$ . Statistical analyses will be performed by the 59MDW Biostatistician using SAS version 9.4 (Statistical Analysis Software, Cary, NC).

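### Does the Shapiro-Wilk switch between parametric and rank tests need a stated trigger and a post hoc rule for the rank branch?

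*Combined protocol and SAP*

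**What the plan says.** The Statistical Analysis section opens with the check: "Continuous variables will be assessed for normality by the Shapiro-Wilks test". It then describes the parametric route. For two time points, "Paired t-tests will be performed to compare the baseline outcome scores with the 12-week outcome scores". For three, "The repeated measures analysis with a Bonferroni post hoc test will be performed to determine significant differences over time". The other route is given in one sentence: "Non-normally distributed data will be presented as median and interquartile range (IQR) and will be analyzed using Wilcoxon signed rank test", together with Friedman's test.

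Two other places under 6. Data Analysis bear on this. The short Data Analysis paragraph mentions only the parametric tests: "These scores are considered outcome variables and will be analyzed using paired t-test and repeated measures analysis". The sample size paragraph is written "for a 2-sided paired t-test with a significance level" of 0.05, with "resilience score mean change = 3, SD = 5". Only the Statistical Analysis section makes the parametric tests conditional on normality.

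**The concern.** The normality check chooses the inferential test as well as the summary statistics. With three scales at three visits, the plan leaves open which quantity is checked (scores, within-subject changes or residuals). It also leaves open how many visits must fail, and whether one scale's failure moves only that scale. The general 0.05 level may be meant as the Shapiro-Wilk cutoff, but this is not stated. Two analysts could send the same data to different tests.

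The two routes are also unequal. The parametric route has an adjusted post hoc test, and the rank route has none stated. If the rank route were followed by three unadjusted pairwise tests per scale, false positives would rise. At stake are a verdict that depends on how the text is read and a pairwise error rate that depends on the branch taken.

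**Working it through.** **Inputs.** From the sample size paragraph: mean change 3, SD 5 (effect size 3/5 = 0.6), two-sided alpha 0.05, 29 completers. The documents give no score distribution, no correlation between visits and no 12-month effect. Assumed here: normal, gamma, lognormal and heavy-tailed (t with 3 df) shapes, correlation 0.5 or 0.7, the change sustained at 12 months, and Shapiro-Wilk at 0.05.

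**The plan's own figure.** Paired t-test power is the probability that |T| exceeds t(0.975; n-1), where T is noncentral t with noncentrality 0.6 × √n. At n = 29 this gives 87.7%. The stated 80% needs only 24 completers (80.4%). The mismatch is a separate matter; here it means the powered test has room to spare.

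**What is tested.** The check is on variables, and the same data are then presented as mean and SD or as median and IQR. The Data Analysis paragraph calls the questionnaire scores the outcome variables. Raw scores are therefore the plain reading. Changes are arguable. Residuals are neither collected nor presented.

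**12-week comparison.** Across all readings and shapes, including switching on changes, the lowest power is 83.3%; the fixed t-test has 83.1% in the same strongly left-skewed setting. With symmetric changes and no effect, every reading rejects in 4.3 to 5.4% of trials.

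**Three-visit comparison.** Power (%) when the switch is on raw scores:

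| Assumed shape | Any visit fails | Two of three | All three | Fixed repeated measures |
|---|---|---|---|---|
| Normal | 89.2 | 90.7 | 90.9 | 90.9 |
| Gamma scores, correlation 0.7 | 83.9 | 87.2 | 89.3 | 91.4 |
| Lognormal scores, correlation 0.7 | 82.9 | 85.8 | 87.9 | 91.1 |
| Heavy-tailed errors, correlation 0.5 | 96.5 | 93.0 | 91.8 | 91.6 |
| Strongly right-skewed changes | 90.8 | 94.3 | 96.8 | 97.0 |

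The largest loss is 91.1 - 82.9 = 8.2 points and the largest gain 96.5 - 91.6 = 4.9 points. With symmetric changes and no effect, rejection is 4.4 to 5.6%.

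**How often the reading alters the verdict.** At mean change 3, comparing only raw-score triggers, they disagree in 0.5 to 4.0% of trials at 12 weeks and 2.0 to 6.3% at three visits (heavy tails not run). With heavy tails and all readings counted, the figures are 2.8 to 6.1% and 3.9 to 6.6%. Restricting to raw-score triggers can only lower these.

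**Post hoc tests.** Under the null with normal data, the chance of at least one false positive per scale is:

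- three unadjusted Wilcoxon tests on every trial: 11.9%
- Wilcoxon with Bonferroni, or only after a significant Friedman test: 3.9%
- paired t-tests with Bonferroni: 4.2%

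The 11.9% supposes that the rank route is always taken. With normal scores and the most sensitive trigger it is taken in 14.4% of trials. A rough mix is 0.144 × 11.9 + 0.856 × 4.2 = 1.7 + 3.6 = 5.3%. Direct simulation of the rule gives 5.5%.

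**The alternative.** Take the parametric tests as fixed and the rank tests as sensitivity analyses, and compare with a switch on changes or residuals:

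- Heavy-tailed changes: about 89% vs 95% at 12 weeks, and 91 to 92% vs 97% at three visits.
- Left-skewed changes: a loss of 2.5 points (89.1 vs 91.6, three visits) to 7.4 points (83.1 vs 90.5, 12 weeks).
- Strongly right-skewed changes: a gain, 94.0 vs 90.0 at 12 weeks and 97.0 vs 82.6 at three visits.

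**The case for a change.** The best case for a change is that no subject has been enrolled on these documents, so a few sentences now would settle the rule before any data exist. Under the widest set of readings the figures are larger. With skewed changes, readings disagree in up to 15.8% of trials at three visits. A residual-based switch rejects in 6.5 to 16.4% of trials at zero mean change, against 5.6 to 8.5% for fixed repeated measures.

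Part of this stands. The trigger is unstated, and so is any adjustment in the rank route. The large figures are weaker. They lean on the residual reading, which the wording hardly supports; in a re-run of the strongly right-skewed setting, keeping only raw-score triggers cut disagreement from 13.4% to 5.4%. They also rest on an extreme assumed response shape. Zero mean change is not a clean null for a rank test when changes are skewed, and some of the repeated measures excess is non-sphericity.

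It is also too strong to say that the 12-month comparison has no test in the rank route. Non-normal data "will be analyzed using Wilcoxon signed rank test and Friedman's Rank Test (non-parametric methods", and nothing confines the Wilcoxon test to 12 weeks. Only its adjustment is missing. Nor do the other two paragraphs conflict with this one: the first is a one-sentence summary, and powering on the planned parametric test is ordinary practice.

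**Conclusion.** No change is needed. The missing details are ones that the biostatistician named in the plan can fill sensibly: check the scores, decide scale by scale, and carry the stated Bonferroni adjustment over to pairwise Wilcoxon tests or run them only after a significant Friedman test. Either post hoc choice holds the per-scale error at about 3.9% under the null with normal data.

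The comparison on which the trial was sized is barely affected (at least 83.3% power under any reading examined). The effect on the three-visit analysis, between about -8 and +5 points of power under raw-score triggers, comes from assumed distributions that the documents neither support nor exclude. Making the parametric analysis primary is a reasonable preference, but its gain or loss depends on a shape nobody knows in advance. For a one-arm, pre/post study described as a possible pilot, a sentence naming the trigger and the rank post hoc adjustment would be harmless tidying. Its absence does not undermine the analysis.

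### The 12-month change is tested only through a Bonferroni post hoc test; Holm on the same three pairs keeps the family-wise guarantee, never rejects less, and adds about 1 to 6 points of power

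*Combined protocol and SAP*

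**What the plan says.** The Statistical Analysis section sets out two layers for normally distributed scores. The first covers 12 weeks only: "Paired t-tests will be performed to compare the baseline outcome scores with the 12-week outcome scores". No multiplicity adjustment is attached to it. The second covers baseline, 12 weeks and 12 months together: "The repeated measures analysis with a Bonferroni post hoc test will be performed to determine significant differences over time". The number of post hoc contrasts is not given. For non-normal scores the section names the Wilcoxon signed rank and Friedman tests and states no post hoc rule.

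The sample-size section powers a single paired comparison. It assumes a "medium effect size (0.6, a resilience score mean change = 3, SD = 5" and states that "35 subjects (29 completed) will achieve 80% power". It names no visit for that change and gives no effect or power for 12 months.

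The hypotheses in section 3 concern a correlation between "SMART program mindfulness training program and increased resilience, decreased stress" and better quality of life. They name no time points.

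**The concern.** Apart from the overall repeated measures test, the 12-month change has no test other than the Bonferroni comparison. With three visits there are three pairs, so each would be judged at 0.05/3 = 0.0167, while the sample size was worked out for one test at 0.05. Single-step Bonferroni is uniformly dominated by Holm on the same contrasts: the family-wise guarantee is the same, and Holm never rejects fewer hypotheses. With about 29 completers, whether a benefit lasts to one year is a thinly powered question. The stated method gives away some power there, so a lasting effect is somewhat more likely to be reported as non-significant than it needs to be.

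**Working it through.** **Inputs from the sample-size section.** Mean change 3, SD of change 5, so d = 3/5 = 0.6; two-sided α = 0.05; 35 enrolled, 29 completing.

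**Assumptions, not in the documents.** Three pairwise contrasts; 29 completers at 12 months; SD 5 for each paired change; correlation r = 0.5 between the 12-week and 12-month changes from baseline; a separate paired standard error for each contrast. With r = 0.5 the SD of the 12-week to 12-month difference is 5 × √(2(1 − 0.5)) = 5, so all three pairs have the same SD.

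**Step 1: the plan's own figure.** Paired t-test power is the probability that a noncentral t with n − 1 df and noncentrality d√n exceeds the two-sided critical value. With n = 29, d = 0.6 and α = 0.05 the power is 0.877, not 0.80. Eighty per cent needs 24 completers (0.804). The stated figure therefore does not reproduce, but it errs towards more power. That is a separate matter from this point.

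**Step 2: the same formula at the post hoc levels (n = 29, d = 0.6).**

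| Two-sided level | Power |
|---|---|
| 0.05 | 0.877 |
| 0.05/2 = 0.025 | 0.800 |
| 0.05/3 = 0.0167 | 0.749 |

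**Step 3: why Holm cannot do worse.** Order the three p-values. Bonferroni compares each with 0.0167. Holm compares the smallest with 0.0167, the next with 0.025 and the largest with 0.05, stopping at the first failure. Every Holm threshold is at least 0.0167, so anything Bonferroni rejects, Holm rejects too. When all three nulls are true, both methods make an error exactly when the smallest p-value falls below 0.0167, so their family-wise error is identical in that case.

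**Step 4: 12-month power on the same three pairs, by simulation.**

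| Change at 12 weeks / 12 months (points) | Bonferroni | Holm | Gain (percentage points) |
|---|---|---|---|
| 3 / 3 | 0.75 | 0.79 | about 4 |
| 3 / 2 | 0.37 | 0.43 | about 6 |
| 1.5 / 3 | 0.75 | 0.76 | about 1 |
| 0 / 3 | 0.75 | 0.78 | about 3 |

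The gain comes mostly from the second Holm step, at 0.025. It is largest when the 12-week pair is likely to be rejected first. It is small in the 1.5 / 3 case, where the 12-month p-value is usually the smallest and still faces 0.0167. For the 3 / 3 case, correlations from 0 to 0.8 leave Holm at 0.78 to 0.79.

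**Step 5: error rates per score when nothing changes (r = 0.5).** The post hoc family alone gives about 4.4% for both methods. Adding the separate unadjusted 12-week t-test gives about 7.4% for both. The swap alters neither.

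**Step 6: the two-contrast alternative.** Restricting the family to baseline vs 12 weeks and baseline vs 12 months, with 3 points at both visits, moves 12-month power from 0.749 to 0.800 by deleting a contrast, and then to 0.852 by using Holm on the two that remain. If the 12-week change is zero, Holm on two contrasts gives 0.80.

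**The case against.** The strongest objection is that Bonferroni over three visits is valid, prespecified and familiar, that the study may serve as a pilot, and that no 12-month power was promised. All of that stands. It makes the point an improvement, not a defect. It does not give a reason to prefer the weaker of two procedures with the same guarantee.

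A second objection is that a repeated measures analysis may use a pooled error term. With 56 df, Bonferroni power in the 3 / 3 case is 0.77 and Holm power about 0.80. The levels shift, but a gain of about 3 points remains.

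A third is that Bonferroni extends directly to simultaneous confidence intervals and Holm does not do so simply. That is fair, but the analysis section plans no such intervals.

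A reader might go further and infer that testing only the two baseline contrasts with Holm lifts 12-month power from 0.75 to 0.85 at the same 5% error rate and at no cost. The documents do not support that reading, for three reasons.

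- The stated aim is differences over time across all three visits. This covers 12 weeks vs 12 months, the direct contrast for whether an early gain is kept. Section 3 names no time points, so it does not make that pair irrelevant.
- The separate 12-week t-test at 0.05 would remain. With it, error per score is about 6.2 to 7.4%. Holding 5% means folding that test into the family, which lowers 12-week power from 0.88 to about 0.80 to 0.86.
- About half of the rise comes from deleting a contrast, and 0.85 also needs a full 3-point change at 12 weeks.

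**Conclusion.** The point holds as a small improvement that costs no data, no contrast and no error control. On the three pairs that the plan appears to intend, Holm in place of Bonferroni keeps the family-wise guarantee of the post hoc test, leaves the plan's overall error where it is, and adds about 1 to 6 percentage points of 12-month power in the settings examined. The dominance of Holm does not depend on any assumption about effects. The sizes do: they need 29 completers at 12 months, SD 5, r = 0.5, separate paired standard errors and the three-pair reading.

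The point applies to normally distributed scores. It does not address multiplicity across the three outcome scores, or the double testing of the 12-week pair. The two-contrast family (12-month power about 0.80 to 0.86 for a 3-point change) is a legitimate option, but it is a choice between questions and not a free gain.

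**What to change.** In the Statistical Analysis section, replace the Bonferroni post hoc wording with:

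> Holm-adjusted post hoc pairwise comparisons of the three visits (two-sided family-wise 0.05 for each score)

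This also settles how many contrasts are in the family. It costs one phrase: no subjects, visits or data are added, all three contrasts stay tested, and Holm needs only the three unadjusted p-values.

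Optional: if the investigators decide that only change from baseline matters, they may limit the family to the two baseline contrasts. They should then say that 12 weeks vs 12 months is descriptive and fold the separate 12-week t-test into the family, accepting 12-week power of about 0.80 to 0.86 in place of 0.88.
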